Baseline Assessment and Screening Procedures: Following in-person informed consent, all potential participants will undergo in-person neuropsychological testing prior to randomization in order to establish baseline cognitive functioning and verify that they are indeed in the early stages of dementia (i.e., "mild" dementia). This testing will take approximately two hours and will be administered and scored/interpreted by the PI, who previously received extensive training in neuropsychological assessment, interpretation, and feedback. Cognitive domains evaluated will include global cognitive status, learning and memory, attention, processing speed, executive function, visuospatial skills, and language. If test results indicate that a participant has early-stage dementia, he or she will then be randomly assigned to the intervention group or wait-list control. For those individuals who meet criteria, assessments measuring aspects of well-being, sense of self, sense of control, and frequency/severity of neuropsychiatric symptoms will also be administered. Specifically, various subtests from the following protocols will be used: Test of Premorbid Function, Wechsler Memory Scale-III, Wechsler Adult Intelligence Scale-Fourth Edition, Trail-Making Test Parts A and B, Stroop Color-Word Test, Controlled Oral Word Association Test, Boston Naming Test, Rey-Osterrieth Complex Figure Test, and Repeatable Battery for the Assessment of Neuropsychological Status. The purpose of the home clinical assessment is to confirm dementia diagnosis and staging, review medication use, and exclude delirium and other conditions as described above. The Neuropsychiatric Inventory, Geriatric Depression Scale, Geriatric Anxiety Inventory, MIDI Sense of Control Scale, Wallhagen Perceived Control Questionnaire, Identity-Alzheimer Moderate Test, and IMAGE Test will also be administered.

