Feedback Session: The potential participant and his/her caregiver will be provided with feedback from the neuropsychological assessment within one week of testing. If the results indicate that the potential participant is cognitively healthy, meets criteria for mild cognitive impairment, or meets criteria for dementia that has advanced beyond the early, or mild, stage, this will be the final session with the potential participant. If the results of the assessment indicate that the potential participant is indeed at a mild stage of dementia, he or she and the PI will work together in a subsequent session to co-design a meaningful activity plan and map out a gradation plan to correspond with

disease progression. The caregiver will be advised on how to modify/grade the activity(ies) as the disease advances.

Randomization and Study Arm Protocol: Persons randomized to the User-Led Meaningful Activity intervention group will begin the treatment protocol (described below) right after randomization. The intervention will consist of 2-3 sessions lasting 60-90 minutes each in which participants identify the basis/topic of the activity plan, receive dementia psychoeducation, and map out an activity gradation plan. There will be a check-in at 8 months. The neuropsychological battery that was administered at baseline will be re-administered 4 months and 12 months after baseline. Persons randomized to the wait-list control group will begin the treatment protocol after four months' time. There will be a check-in at 8 months. The neuropsychological battery that was administered at baseline will be administered 4 months and 12 months after baseline.

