Protocol Title: User-Led Meaningful Activity and Early-Stage Dementia

Document Title: Statistical Analysis Plan

NCT: NCT05159869

Document Date: 21AUG2025

Statistical Analysis Plan

The study followed a randomized, two-arm parallel design. Seventy (70) dyads comprising community-dwelling individuals with early-stage dementia and their primary caregivers were assigned to treatment or wait-list control. Treatment group participants received the co-designed meaningful activity intervention, and all dyads were reassessed at four months from baseline. After four months, wait-list control dyads received the same intervention and were retested four months later (i.e., eight months from baseline).

Analyses were based on the Intent-To-Treat (ITT) principle, including every patient who was randomized. All tests were performed at two-tailed significance $\alpha=0.05$. First, chi-squared and t-test tests were used to compare intervention and control dyads on baseline characteristics. The primary hypothesis held that a co-designed meaningful activity intervention would significantly decrease the frequency and intensity of neuropsychiatric symptoms (NPS) and slow cognitive decline across multiple domains (i.e., memory and learning, executive function, visuospatial abilities, attention, language, processing speed). The secondary hypothesis was that a co-designed meaningful activity intervention would significantly increase emotional well-being (e.g., reduce depression and anxiety) and strengthen self-identity. To test the hypotheses, main treatment effects at four months were examined using analysis of covariance (ANCOVA). Given prior research linking caregiver characteristics to ratings of neuropsychiatric and psychosocial outcomes, caregiver sex, race/ethnicity, education, and relationship to the person living with dementia (PLWD) were identified a priori as covariates. Standardized effect sizes (d) were calculated as the adjusted mean difference between groups divided by the square root of the model's mean square error (MSE).

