To evaluate whether wait-list control participants derived benefits comparable to those of the meaningful activity group after receiving the intervention, change scores were examined from 4 months (T2) to 8 months (T3) in the wait-list control group and compared with change scores from baseline (T1) to 4 months (T2) in the meaningful activity intervention group. Analyses were conducted using the same ANCOVA framework applied in the primary analysis. It was hypothesized that the magnitude of treatment effects would be similar across groups, reflecting replication of benefit, and therefore the between-group difference in change would not be statistically significant.

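### The four-month ANCOVA lists only caregiver covariates, not each outcome's baseline score, and does not name the response; fitted as listed, it loses precision on either reading and leaves the scale of d unclear

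*SAP*

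**What the plan says.** The SAP's second paragraph tests the primary and secondary hypotheses in one comparison: "main treatment effects at four months were examined using analysis of covariance (ANCOVA". The covariate statement is that "caregiver sex, race/ethnicity, education, and relationship to the person living with dementia (PLWD) were identified a priori as covariates". The reason given is earlier evidence linking caregivers to how neuropsychiatric and psychosocial outcomes are rated. The paragraph does not list the outcome's baseline score, does not say it was left out, and does not name the response variable. The effect size d is the adjusted group difference "divided by the square root of the model's mean square error (MSE".

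The SAP's final paragraph compares change scores for the wait-list group with those for the intervention group and adds: "Analyses were conducted using the same ANCOVA framework applied in the primary analysis". That makes a change response possible for the main test without establishing it.

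Baseline data were planned. For cognition, the Protocol (Baseline Assessment and Screening Procedures) says "all potential participants will undergo in-person neuropsychological testing prior to randomization in order to establish baseline cognitive functioning", and its section on randomization and study arms says "The neuropsychological battery that was administered at baseline will be re-administered 4 months and 12 months after baseline". For the other scales, the baseline section says "assessments measuring aspects of well-being, sense of self, sense of control, and frequency/severity of neuropsychiatric symptoms will also be administered". That sentence follows the one on random assignment, so the order of these scales relative to randomization is not explicit.

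**The concern.** A participant's baseline score usually predicts the same score four months later better than caregiver characteristics do. Without it, the variation it would explain stays in the error term, and any chance baseline difference between the arms goes uncorrected. The stated rationale for the caregiver covariates also gives no reason to expect them to explain cognitive test scores, which are part of the primary hypothesis.

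Two things are at stake. The first is precision, in a trial of only 70 dyads. The second is interpretation. The Protocol (Follow-Up Data Collection Periods) presents estimation of a four-month effect size as a purpose of the design, and d is tied to the residual variance of a model that is not fully stated. A reader planning a later trial could not tell what scale those d values are on.

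**Working it through.** **Inputs from the documents.** 70 dyads in two arms (SAP, first paragraph); "All tests were performed at two-tailed significance" 0.05. The documents give no r, SD, target effect, power or allocation ratio, so there is no stated figure to reproduce.

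**Assumed inputs.** 35 per arm, equal SDs at both visits, caregiver covariates that explain nothing, r from 0.3 to 0.8, and a true difference of 0.5 SD for power.

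**Residual variance, in units of the four-month variance**
- Four-month score, no baseline: 1
- Change, no baseline: 2(1 − r)
- Baseline-adjusted: 1 − r²

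**Proportional SE reduction from adding baseline**
- Against score: 1 − √(1 − r²)
- Against change: 1 − √((1 + r)/2)

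At r = 0.7 these are 1 − √0.51 = 0.286 and 1 − √0.85 = 0.078.

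| r | SE cut, score | SE cut, change | Power: score | Power: change | Power: adjusted |
|---|---|---|---|---|---|
| 0.3 | 5% | 19% | 54% | 41% | 58% |
| 0.5 | 13% | 13% | 54% | 54% | 66% |
| 0.7 | 29% | 8% | 54% | 76% | 82% |
| 0.8 | 40% | 5% | 54% | 90% | 93% |

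Power is from the noncentral t distribution. Simulation with four inert covariates (5,000 trials per setting, complete data) gave values about 2 to 4 points lower in every column (at r = 0.7: 52%, 72% and 79%) but the same pattern.

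**Equivalent sample size.** The number of baseline-adjusted dyads matching 70 unadjusted ones is 70(1 − r²) for score: 63.7, 52.5, 35.7 and 25.2 at r = 0.3, 0.5, 0.7 and 0.8. For change it is 70(1 + r)/2: 45.5, 52.5, 59.5 and 63.0.

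**Sensitivity to the assumptions.**
- If enrolling only mild dementia narrows the baseline SD to k = 0.8 of the four-month SD, the change variance becomes 1 + k² − 2rk. The change-reading cut is then about 6%, 1% and 0% at r = 0.5, 0.7 and 0.8, and the two readings tie at r = k/2 = 0.4. The score-reading cut depends only on r.
- If caregiver covariates explain the same 20% of both scores, the partial correlation is (r − 0.2)/0.8. At r = 0.5 the cuts are 7% (score) and 17% (change); at r = 0.6 both are 13%.

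**Chance imbalance.** The SE of the baseline gap is √(2/35) = 0.239 SD, so a gap above 0.25 SD in either direction has probability 0.296. Such a gap shifts a score estimate by r × 0.25 and a change estimate by −(1 − r) × 0.25. At r = 0.7 that is +0.175 and −0.075 SD; at r = 0.5 it is +0.125 and −0.125 SD.

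**Scale of d.** For one true difference of 0.30 SD at r = 0.7, d is 0.30/1 = 0.30 (score), 0.30/√0.6 = 0.39 (change) or 0.30/√0.51 = 0.42 (baseline-adjusted).

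**Bias.** With complete data, all three models averaged −0.50 for a true −0.50. In a separate simulation (6,000 trials per r, r = 0.5 to 0.8, complete data) type I error was 0.046 to 0.054. In a dropout scenario, control dropout was a flat 12%, while treated participants with higher baseline scores left more often. At r = 0.7 the averages were −0.59 (score), −0.46 (change) and −0.50 (baseline-adjusted). The adjusted model holds there because dropout depended only on arm and baseline; it would not repair dropout driven by the unseen four-month outcome.

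**The case against.** The strongest reply is that nothing shows baseline was left out. An ANCOVA of a repeatedly measured outcome is commonly baseline-adjusted, and the covariate sentence justifies the caregiver variables without claiming to be the whole model. This stands. A reader might infer from the list that the baseline score was excluded, but the documents do not say so. It does not close the point: ANCOVA needs only some covariate, the SAP gives a specific list without baseline, and the response would still be unnamed.

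A second reply is that a randomized comparison is valid without baseline adjustment. A reader might infer that omitting baseline makes the four-month test biased or invalid. The documents do not support that: with complete data, or dropout unrelated to outcome, the estimate is unbiased on average and type I error is held. The condition matters, because the SAP claims intention-to-treat on everyone randomized but gives no missing-data method.

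A third reply is that a change response already uses baseline, so only the score reading loses anything worth noting. That fails in general. With equal SDs the two readings lose equally at r = 0.5, and change loses more below it. With outcomes spanning neuropsychiatric symptoms, several cognitive domains, mood and identity, no single high r can be presumed. What stands is that at high r, or with a narrowed baseline SD, the change-reading loss is small, and it vanishes when the slope of four-month score on baseline is 1.

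**Conclusion.** The point holds as a specification gap with a conditional cost. The gap is certain: the response is unnamed and the outcome's baseline score is not listed. The loss of precision follows only if the model was fitted as listed. In that case it arises on either reading; with equal SDs the score reading loses more above r = 0.5 and the change reading more below it. Over r = 0.3 to 0.8 the avoidable share of the standard error runs from about 5% to 40% for score and from 19% down to 5% for change. These sizes are illustrative. They rest on assumed correlations, equal SDs, equal allocation and uninformative caregiver covariates, and the sensitivity cases show the crossover moving to 0.4 or 0.6.

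The uncertainty over d holds whichever model was used, until that model is stated. This should be fixed, but it does not by itself overturn the randomized comparison.

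**What to change.** State the response variable and include each outcome's baseline score, alongside the four caregiver variables, in the four-month ANCOVA.

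- **If baseline was already in the model:** say so. Only SAP wording changes and nothing is re-run.
- **If it was not:** refit each four-month model with baseline added, label the refit post hoc, and show it beside the original results. The cost is one degree of freedom per model, on data already collected. With baseline as a covariate, score and change responses give the same treatment estimate, SE, MSE and d, because subtracting baseline from the response only lowers its coefficient by 1. One refit therefore settles both open questions.
- **Before refitting the neuropsychiatric, mood, control and identity scales:** check assessment dates against randomization dates to confirm that baseline came first.
- **In reporting:** give the raw adjusted difference with its 95% CI and the outcome SD, and name the model behind each d. The refit itself raises d for the same difference, so d alone is not enough for planning a later trial.

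This covers only the randomized four-month comparison. No change is proposed to the wait-list comparison in the SAP's final paragraph.

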Protocol Title: User-Led Meaningful Activity and Early-Stage Dementia

Document Title: Study Protocol

NCT: NCT05159869

Document Date: 03DEC2021

Study Protocol

The clinical trial phase will be a pilot randomized, controlled trial exploring the design and feasibility of a novel approach to dementia intervention development. The randomized, controlled pilot study compares the efficacy of the co-creation of a tailored activity plan with a wait-list control group. Using a two-group randomized, parallel design, 60 persons with early-stage dementia will be assigned to treatment or wait-list control.

Recruitment: Potential participants will be recruited through 1) the Johns Hopkins University Maximizing Independence (MIND) at Home study, 2) the Johns Hopkins Bayview Medical Center Memory Clinic, 3) community-based social agencies such as the Alzheimer's Association, and 4) independent and semi-independent residences designed for older adults including continuing care retirement communities and assisted living facilities. Recruitment efforts are aimed at persons living with early-stage dementia and their informal/unpaid caregivers using three main forms of messaging: (a) flyers, (b) a description of the study that was prepared originally for clinicaltrials.gov, and (c) in-person recruitment presentations. All recruitment materials describe the general nature and goals of the research and provide information about what participation involves and monetary compensation. The Principal Investigator (PI) is listed as the source for additional information and addressing questions in all materials.

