caregiver as the dementia progresses. This session will also involve a discussion of how to modify the activity and follow the gradation plan through the stages of dementia. Carer participation is essential for the delivery and sustainability of the intervention, as the PLWD will have increasing difficulty with activity initiation over time.

Study Reminders: The PI and study staff will contact study participants monthly via phone to inquire about how the implementation of the meaningful activity plan is going, answer any questions, and elicit feedback related to intervention feasibility and acceptability. For persons in the wait-list control group, these phone check-ins will also occur each month during the four months prior to co-design and intervention implementation, but the focus will be reminding them of their start-date and that they are still enrolled in the study and study staff are looking forward to working with them.

Follow-Up Data Collection Periods: Treatment group participants will receive the intervention, and will be reassessed at 4 months and 12 months from baseline. There will also be a "check-in" after 8 months' time. Four months after their baseline, wait-list controls will receive the same intervention and will be reassessed, and again at 12 months from baseline. There will be an 8-month visit for wait-list controls. This design allows for estimation of effect sizes using a randomized two-group design at four months, confirmation of treatment gains for wait-listed participants from 4-12 months, and evaluation of intervention acceptability.

Feasibility and Acceptability: Feasibility and acceptability as perceived by the PLWD and the caregiver will be assessed through semi-structured interviews and rating scales. Regarding rating scales, the PLWD and caregiver will separately be asked to rate intervention feasibility and acceptability using the following questions on a three-point Likert scale (1 = not at all, 2 = somewhat, 3 = very): 1) Was the meaningful activity plan useful? 2) How easy was it to incorporate the activities into your routine? 3) How easy was it to follow the instructions for adjusting the activities if needed? 4) Did the meaningful activity plan increase the amount you did enjoyable activities? 5) How satisfied were you with the meaningful activity plan? 6) Was participation in this study burdensome? 7) Do you think you will continue using the activity plan now that you are done with the study?

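### Does dividing by the root mean square error make the SAP's standardized effect size misleading?

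*SAP*

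**What the plan says.** The second paragraph of the SAP sets out the whole calculation. For the model, "main treatment effects at four months were examined using analysis of covariance (ANCOVA", with the abbreviation then closed. For the adjustment, "caregiver sex, race/ethnicity, education, and relationship to the person living with dementia (PLWD) were identified a priori as covariates". The next sentence defines d as "the adjusted mean difference between groups divided by the square root of the model's mean square error (MSE". The sample is given in the SAP's opening paragraph: "Seventy (70) dyads comprising community-dwelling individuals with early-stage dementia and their primary caregivers were assigned to treatment or wait-list control".

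The protocol explains why an effect size is wanted. Its opening paragraph says "The clinical trial phase will be a pilot randomized, controlled trial exploring the design and feasibility of a novel approach", and its section on follow-up data collection periods says "This design allows for estimation of effect sizes using a randomized two-group design at four months".

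Neither document gives an R2, an outcome SD, a target d or a power calculation. Neither mentions a second effect size standardized on the outcome's own SD.

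**The concern.** Readers often take d to be a mean difference in units of the between-person SD of the outcome. The SAP's denominator is not that. The MSE of an ANCOVA is the variance that remains after the covariates, so its square root is normally the smaller of the two SDs and the resulting d the larger.

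Two consequences would matter if they were real and sizeable. First, this is a pilot and effect sizes are one of its stated products. An inflated d carried into the planning of a later trial could make that trial too small. Second, the covariates may explain more of some outcomes than of others, so d values for neuropsychiatric symptoms, cognition and well-being might not be comparable with one another.

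**Working it through.** The plan has no figure of its own to reproduce, so the check is how far apart the two versions of d can be, and whether anything depends on the gap.

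**Inputs.** From the SAP: d = adjusted difference / sqrt(MSE), an ANCOVA with four caregiver covariates, and 70 dyads. Assumed, because the documents are silent: 35 dyads per arm, complete four-month data, the raw four-month score as dependent variable, and R2 values of 0.05, 0.10 and 0.20.

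**Step 1: the ratio.** With the numerator held fixed,

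(difference / sqrt(MSE)) / (difference / pooled SD) = pooled SD / sqrt(MSE), which is about 1/sqrt(1 - R2).

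Here R2 is the within-arm share of outcome variance explained by the covariates. The relation is exact in a sample when R2 is adjusted for degrees of freedom.

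| Assumed R2 | 1/sqrt(1 - R2) | d of 0.40 becomes | Shift |
|---|---|---|---|
| 0 | 1.000 | 0.400 | 0 |
| 0.05 | 1.026 | 0.410 | 0.010 |
| 0.10 | 1.054 | 0.422 | 0.022 |
| 0.20 | 1.118 | 0.447 | 0.047 |

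Simulated ANCOVAs with 70 dyads and 4, 7 or 10 covariate terms gave mean ratios of 1.001 to 1.002 at R2 = 0, 1.026 to 1.029 at 0.05, and 1.119 to 1.123 at 0.20. In a single trial even the direction is not certain. At R2 = 0.05 the root MSE exceeded the pooled SD, making the SAP's d the smaller one, in about 24% to 30% of simulated trials.

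**Step 2: the shift against the precision of d.** For d = 0.40, the 95% half-width is 1.96 x sqrt(2/35 + 0.40^2/(2 x 70)) = 1.96 x sqrt(0.0571 + 0.0011) = 0.473. The shifts of 0.010, 0.022 and 0.047 are 2.2%, 4.6% and 10.0% of it.

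**Step 3: dependence on the model.** The SAP's final paragraph analyses change scores and says the ANCOVA approach is the one used in the primary analysis, so a change-score primary model cannot be ruled out. With equal SDs at both visits, correlation r between them and no covariate effect, the ratio to the four-month SD becomes 1/sqrt(2(1 - r)):

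- r = 0.4: 1/sqrt(1.2) = 0.91
- r = 0.5: 1/sqrt(1.0) = 1.00
- r = 0.7: 1/sqrt(0.6) = 1.29

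On that reading the SAP's d can be the smaller one. If the baseline score were instead a covariate, the ratio would be 1/sqrt(1 - r^2), or 1.15 at r = 0.5. A fixed excess of 3% to 12% therefore cannot be attributed to the plan.

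**Step 4: the alternatives.** The pooled four-month SD is measured after treatment. If response varied so that the treated-arm SD were k times the control SD, the pooled SD would be multiplied by sqrt((1 + k^2)/2). That is 1.051 at k = 1.1 and 1.105 at k = 1.2, and a d of 0.40 would fall to 0.38 or 0.36. The root MSE comes from the same visit and rises too, so this does not favour either one. The baseline SD avoids the difficulty, but entry is restricted to mild dementia, which may narrow it. At R2 = 0.10 it gives a larger d than the SAP's whenever it is below sqrt(0.90) = 95% of the four-month SD. No candidate denominator is free of distortions of this size.

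**Step 5: what depends on the choice.** The test of treatment uses the adjusted difference and its standard error, and d is computed afterwards. No threshold, progression rule or sample-size calculation in either document uses d. For planning a later trial with the same ANCOVA, a difference in residual-SD units is a suitable input.

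**The case for a change.** The best argument for the concern is comparability across outcomes. The SAP justifies its covariates by earlier work on caregiver characteristics and ratings of neuropsychiatric and psychosocial outcomes, and does not mention cognitive tests. It nevertheless describes one model and one formula for all hypotheses. If caregiver covariates explain more of the rated outcomes than of the test scores, d is stretched more for the former. Giving the outcome SD, or a second d, would remove the doubt at almost no cost.

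Part of this stands. Someone setting these d values beside others standardized on the outcome SD, or planning a trial with different covariates, would need to know that SD. But the documents contain nothing to show that R2 differs between outcomes or is material for any. A lack of labelling is not a fair complaint either: the SAP calls the difference adjusted, ties the MSE to the model, and lists the covariates in the sentence before.

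A second argument is that the excess could be much larger if the baseline score is in the model: an illustrative R2 of 0.30 to 0.60 gives 20% to 58%. The SAP does not list a baseline covariate. If there is doubt about that, it concerns how the primary model is specified. It does not make the definition of d wrong.

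**Conclusion.** The concern does not hold. Its algebra is correct, but it identifies no error, contradiction or omission: the effect size is fully defined, the definition is a recognised one, and it suits a later trial analysed in the same way. What remains is a preference for an additional column of results, which would change no test, decision or conclusion.

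The possible gap is nil if the covariates explain nothing. At an assumed R2 of 0.05 to 0.20 it is 0.01 to 0.05 on a d of 0.40, small beside the sampling error of a 70-dyad trial. That size rests on equal arms, complete data, raw four-month scores and no baseline covariate, none of which the documents settle. The conclusion does not rest on the size alone, because the SAP lets any reader see which SD was used.

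### The wait-list replication contrast compares uncontrolled changes over different four-month windows, so it compares treatment effects only if non-treatment change is equal in both, which is unstated and doubtful for cognition

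*SAP*

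**What the plan says.** The last paragraph of the SAP sets out the replication analysis. Its purpose is given as "To evaluate whether wait-list control participants derived benefits comparable to those of the meaningful activity group after receiving the intervention". For this, "change scores were examined from 4 months (T2) to 8 months (T3) in the wait-list control group" and these are "compared with change scores from baseline (T1) to 4 months (T2) in the meaningful activity intervention group". On the model it says only "Analyses were conducted using the same ANCOVA framework applied in the primary analysis". The covariates named for the primary analysis are all caregiver characteristics, and no term for period or test occasion is named. The SAP expects that "the magnitude of treatment effects would be similar across groups" and concludes that "therefore the between-group difference in change would not be statistically significant".

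Two protocol sections bear on the windows. Under Feedback Session, the participant and caregiver "will be provided with feedback from the neuropsychological assessment within one week of testing". Under Randomization and Study Arm Protocol, for the intervention arm, "The neuropsychological battery that was administered at baseline will be re-administered 4 months and 12 months after baseline"; the wait-list arm has the same battery schedule, and both arms have a check-in at month 8. The SAP reports a further wait-list test at month 8 without listing the instruments.

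**The concern.** A treatment effect is a change relative to what would have happened without treatment. In the four-month primary analysis the wait-list arm supplies that comparison. In the replication analysis neither change has an untreated comparator from the same window, and randomization does not balance two windows that are not concurrent.

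For cognition, which is part of the primary hypothesis, two features make the windows unlike.

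- **Practice.** The intervention arm's change spans the first repeat of the battery. The wait-list change appears to span the second.
- **Feedback.** Both arms receive the baseline results soon after the first cognitive testing. That falls inside months 0-4 and outside months 4-8.

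At stake is the claim that benefit was replicated. A period difference could make equal effects look unequal, or offset a real difference in effects. This is separate from whether non-significance shows similarity: an equivalence test on the same contrast would carry the same bias.

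**Working it through.** The documents give no power, SD, margin or expected difference for this contrast, so there is no figure of the plan to reproduce.

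**1. What the contrast estimates.** Let tauI and tauW be the treatment effects in the intervention and wait-list arms. Let pi1 and pi2 be all non-treatment change in months 0-4 and months 4-8. The SAP describes three mean changes:

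- intervention, T1 to T2: tauI + pi1
- wait-list, T1 to T2 (untreated): pi1
- wait-list, T2 to T3: tauW + pi2

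The planned contrast is the first minus the third: (tauI - tauW) + (pi1 - pi2). Three means carry four unknowns (rank 3 of 4). tauI is estimable from the first two lines. tauW and tauI - tauW are not.

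If pi1 = pi2 is assumed, tauW is the wait-list T2-T3 change minus its T1-T2 change, and tauI - tauW reduces exactly to the planned contrast. The analysis is therefore valid under that assumption and not otherwise.

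**2. Does progression break the assumption?** Both windows last four months. At a constant rate of decline the two changes are equal and cancel. Only a changing rate leaves a remainder. For example, with f(t) = -0.1t - 0.01t², the change over months 0-4 is -0.56 and over months 4-8 is -1.44 + 0.56 = -0.88, a gap of 0.32 units. The curve is illustrative; neither document says that the rate changes.

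**3. Size, under assumed inputs.** The SAP gives 70 dyads but not the split, so 35 per arm is assumed. Also assumed are a test-retest correlation r of 0.7-0.8 and a total period difference of 0.1-0.2 outcome SD. Two-sided alpha of 0.05 is from the SAP.

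SE of the difference in change = sqrt(2(1 - r)) × sqrt(2/35):

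- r = 0.7: 0.775 × 0.239 = 0.185 SD
- r = 0.8: 0.632 × 0.239 = 0.151 SD

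With tauI = tauW, the probability of a significant result is Phi(-1.96 + b) + Phi(-1.96 - b), where b = period difference / SE:

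| r | Period difference (SD) | b | Probability of significance |
|---|---|---|---|
| 0.7 | 0.1 | 0.54 | 8.4% |
| 0.7 | 0.2 | 1.08 | 19.1% |
| 0.8 | 0.1 | 0.66 | 10.1% |
| 0.8 | 0.2 | 1.32 | 26.3% |

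Without a period difference it is 5%. The calculation leaves out the caregiver covariates. These could alter the SE, but they do not separate period from arm.

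**The case against.** The strongest reply is that the practice bias, if it runs as expected, works against the sponsor. If the first retest brings the larger gain, months 0-4 look better, the contrast moves toward a difference, and the predicted non-significant result becomes harder to obtain. A weak or absent wait-list effect would not be hidden. Hiding it needs a period difference of the opposite sign: in units of the SD of change, effects of 0.5 and 0 with a period difference of -0.5 give an expected contrast of zero and non-significance 95% of the time. At r = 0.7-0.8 that is 0.5 × 0.775 to 0.5 × 0.632, or about 0.39-0.32 outcome SD, beyond the range assumed above. This stands as far as practice goes. The direction of any feedback effect is unknown, and a false finding of failed replication is still an error.

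It is also fair that every input to the size is assumed, that the low end (8% against 5%) is small, that a third cognitive testing at month 8 is inferred, and that this is a supplementary analysis in a pilot.

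A reader might infer more than the documents support:

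- **That later disease stage by itself biases the contrast.** Constant-rate decline cancels.
- **That all outcomes are affected alike.** Practice concerns performance tests. For symptom and mood ratings, the protocol does not say whether the baseline rating came before or after feedback.
- **That the two windows contain different survivors.** Neither document reports dropout or restricts this analysis to completers, and the SAP states an intent-to-treat principle covering everyone randomized.
- **That the result cannot be interpreted at all.** It can, under a stated equal-period assumption.

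**Conclusion.** The point holds in limited form. Arm and window are completely aliased in the replication contrast, no named covariate separates them, and the equal-period assumption on which the comparison of effects depends is not stated. The aliasing follows from the SAP's own description and needs no numerical assumption.

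That the assumption is doubtful is supported for the cognitive outcomes, by the order of testing (with month 8 read as a third testing) and the timing of feedback. For symptom and mood ratings a bias is possible but not shown.

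The 8-26% range shows what a modest period difference would do under the assumed split, correlations and shift; it is not an estimate for this trial. The randomized comparison at four months, which tests both hypotheses, is untouched. The change is worth making because this contrast is the SAP's only stated basis for claiming replication of benefit.

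**What to change.** 1. State in the SAP and the report that the T2-T3 versus T1-T2 contrast compares treatment effects only if non-treatment change is equal in the two windows.
2. Label the contrast descriptive. Do not claim replication, or failed replication, of cognitive benefit from it.
3. Where both arms have the outcome at a common later visit, add a comparison of change from month 4 between the randomized arms as supportive evidence. Month 12 qualifies if the battery was given as the protocol schedules; month 8 qualifies only if the outcome was captured in both arms. Wait-list catch-up would be the sign of replication.
4. State the limits of that comparison. Waning or further gain in the intervention arm also moves the gap, and if only the wait-list arm was tested at month 8, its month-12 cognitive scores carry one extra test exposure. For these reasons it supports the descriptive contrast and does not replace it.

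The wait-list arm's untreated change over months 0-4 does not remove the problem, since using it to isolate tauW needs the same equal-period assumption.

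The cost is a few sentences of wording and, where the data exist, one further model. No new visits are needed. The SAP mentions no month-12 results and no month-8 test of the intervention arm, so availability must be confirmed first; items 1 and 2 do not depend on it.
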